## Clinical Study Protocol

### Zr-TLX250-003

Version: 8.0  
Date: 01-Apr-2022

- Day 0 pre-dose
- Day 5 ± 2 days
- Final study visit: Day 42 ± 7 days p.a. (for patients with nephrectomy ≤ 28 days p.a.)
- Final study visit: 35 ± 7 days after surgery (for patients with nephrectomy > 28 days p.a.)

Laboratory assessments will be performed by a central laboratory. Because of the potential for radioactivity in some blood samples, the laboratory must adhere to their SOPs and/or any guidance and regulations for handling radioactive substances.

Samples will be tested for the following parameters:

**Haematology:** haemoglobin, haematocrit, mean corpuscular volume (MCV), mean corpuscular haemoglobin (MCH), white blood cell count (total and differential: leukocytes, neutrophils, eosinophils, basophils, lymphocytes, monocytes), red blood cells, platelets

**Biochemistry:** sodium, potassium, chloride, calcium, glucose, creatinine, urea, albumin, total bilirubin, aspartate transaminase (AST), alanine transaminase (ALT), alkaline phosphatase, gamma-glutamyl transferase (GGT), lipase, amylase, total protein

**Clotting status:** prothrombin time (quick), reagent-independent prothrombin ratio (international normalised ratio; INR), activated partial thromboplastin time (aPTT).

**Immunogenicity:** HACA.

**Urinalysis:** density, pH, protein, glucose, blood, urobilinogen, erythrocytes, leukocytes, ketones, bilirubin, nitrite.

A serum β-HCG pregnancy test will be performed only in premenopausal women at screening. Confirmation of the negative result will be done with a urine pregnancy test within 24 hours before administration of the study drug on Day 0 and at the Day 42 (± 7 days) time point (see Section 8.1.5).

The investigator will sign each laboratory assessment to confirm review of the results. Clinically relevant values have to be highlighted as “c.s.” (“clinically significant”). The results will be sent back to the investigational sites and be included in the patient’s eCRF.

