### 8.8.7 HACA Determination in Serum

In order to detect possible formation of antibodies against girentuximab, serum samples will be collected at Screening, on Day 42 ± 7 days p.a. and at the final study visit.

The final study visit will be conducted in relation to the scheduled nephrectomy.

- i) If the scheduled nephrectomy occurs > 28 day p.a. (i.e., between 28 and 90 days p.a.), the final study visit and the blood draw for HACA serum sample will be on Day 35 ± 7 days *after surgery*.
- ii) If the scheduled nephrectomy occurs ≤ 28 days p.a. (i.e. within 28 days p.a.), the final study visit and the blood draw for HACA serum sample will be on Day 42 ± 7 days *after administration*.

Blood sampling will be  $\leq 3$  mL per sample.

An approximately 2 mL blood sample will be collected in an unheparinized (clotted) tube, stored overnight at 2-8°C and centrifuged at 1000-2000 rpm for 10 minutes. Three 200  $\mu$ L serum aliquots will be transferred into three separately labelled 2 mL cryo-vial and stored at -20°C. Please refer to the central laboratory manual for details on shipping.

The presence of HACA in sera of patients will be tested quantitatively and qualitatively using validated ELISAs in the Bioanalytics Department of Agilex Biolabs Pty Ltd, South Australia, Australia.

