10.4.2 Laboratory results

Haematology, Biochemistry, Clotting parameters, Urinalysis and Immunogenicity data will be provided in a listing and summarised in tables. Clinical significance will be presented as a flag on the laboratory listings. Change from baseline will be calculated and statistical significance will be tested using Wilcoxon signed-rank test. Figures to show laboratory results trend over time will be provided.

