10.5 Analysis of Efficacy

10.5.1 Primary and Key Secondary Variables (Sensitivity and Specificity)

Within this trial, two co-primary endpoints (sensitivity and specificity) shall be analysed for each reader.

The analysis for sensitivity uses only those patients with a positive histopathological diagnosis of clear cell renal cell carcinoma. These are expected to be about 70% of the included patient population. Sensitivity of ⁸⁹Zr-TLX250 will be considered adequate if the **lower boundary of a 95% Wilson (score) confidence interval for sensitivity is higher than 0.7** for at least the same two of three independent readers.

The analysis for specificity uses only those patients with a negative histopathological diagnosis of clear cell carcinoma. These are expected to be about 30% of the included patient population. Specificity of ⁸⁹Zr-TLX250 will be considered adequate if **the lower boundary of a 95% Wilson (score) confidence interval for specificity is higher than 0.68** for at least the same two of three independent readers. Two-sided tests will be consistently used in the evaluation.

To account for multiplicity and to control Type I error under the paradigm of two co-primary endpoints sensitivity and specificity will each be estimated at the 5% significance level. For the study to be deemed successful, the lower limit of the 95% Wilson confidence interval for both sensitivity and specificity must exceed their respective pre-specified thresholds.

Assuming the null hypothesis is rejected for both co-primary endpoints, formal statistical testing will proceed to the family of Key Secondary Endpoints (i.e., sensitivity and specificity in the cT1a group). Within this family, the fixed-sequence method will first assess sensitivity, followed by specificity. Results pertaining to specificity will only be considered formal evidence if the null hypothesis pertaining to sensitivity is rejected.

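### SAP 10.4.2 applies a signed-rank test of change from baseline to HACA without exemption; that test does not estimate how many patients form antibodies, and no treatment-emergent incidence with a confidence interval is planned (minor)

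*SAP*

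**What the plan says.** SAP 10.4.2 opens with the data it covers: "Haematology, Biochemistry, Clotting parameters, Urinalysis and Immunogenicity data will be provided in a listing and summarised in tables". After a sentence on flagging clinical significance it continues: "Change from baseline will be calculated and statistical significance will be tested using Wilcoxon signed-rank test". The test sentence does not name HACA, but no data type in the list is excluded from it. Protocol 8.8.3 identifies immunogenicity with HACA.

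Protocol 8.8.7 gives the purpose of the sampling, "In order to detect possible formation of antibodies against girentuximab", and the schedule: "serum samples will be collected at Screening, on Day 42 ± 7 days p.a. and at the final study visit". It also describes the assay output: "The presence of HACA in sera of patients will be tested quantitatively and qualitatively using validated ELISAs". Each patient may therefore have both a positive/negative result and a reading.

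SAP 9.2.6 names HACA testing as a safety variable and adds nothing further. SAP 10.1 plans counts and percentages for categorical data in general, with patients with non-missing data as the denominator. Protocol 9.2.3 describes the analyses of primary and secondary variables as descriptive, so the laboratory significance test appears only in the SAP.

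Section 10.4.2 does not state the significance level, the sidedness, exact or asymptotic p-values, the treatment of zero changes, or which post-dose HACA sample is compared with screening. The nearest statements are in SAP 10.5.1, on efficacy: "Two-sided tests will be consistently used in the evaluation" and "sensitivity and specificity will each be estimated at the 5% significance level".

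**The concern.** HACA sampling asks a question about individuals: which patients, and what share, develop antibodies after one dose of a chimeric antibody. The signed-rank test asks whether paired changes are centred on zero across the group. When most patients do not change and a few change a great deal, the two questions have different answers.

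Three features of the test matter here. In its usual form it discards zero changes, so the number of patients who stayed negative plays no part. A falling titre in a patient positive at screening counts against a true seroconversion. And a p-value, whichever way it falls, gives no incidence and no upper bound.

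The signed-rank test is also the only inference that the plan names for HACA. A non-significant result could be quoted in a report as evidence of no immunogenicity, which it would not be.

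**Working it through.** The plan gives no figure for this test, so there is none to reproduce.

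**Inputs**
- Test: Wilcoxon signed-rank on change from baseline (SAP 10.4.2).
- Two-sided: taken from SAP 10.5.1. Alpha 0.05: an assumption, since the documents state 5% only for the co-primary endpoints.
- Planned patients: 252 (protocol) or 300 (SAP section 6). The number with paired HACA samples is not given. Using 252 and 300 as denominators assumes that everyone has them.
- Number of seroconversions k: not given. Values around five are used for illustration.

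**A. Negative results carry the same value at both visits (zero change)**

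With zeros dropped and all k remaining changes upward, only one of the 2^k equally likely sign patterns is as extreme in that direction. The smallest exact two-sided p is therefore 2/2^k:

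| k | 2/2^k |
|---|---|
| 3 | 0.250 |
| 4 | 0.125 |
| 5 | 0.0625 |
| 6 | 0.031 |
| 7 | 0.016 |

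Six is the first count that can fall below 0.05. Tied changes give the same exact values at k = 5 and k = 6. The number of unchanged patients does not enter: five of 20 and five of 300 both give 0.0625. With six rises and one fall, p is 0.031 if the fall is the smallest change and 0.297 if it is the largest.

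The result depends on options that 10.4.2 leaves open. For k = 5 the signed-rank statistic is 15, its null mean 7.5, and its null standard deviation √(5×6×11/24) = 3.708.
- Normal approximation, no continuity correction: z = 7.5/3.708 = 2.02, p = 0.043.
- With continuity correction: z = 7.0/3.708 = 1.89, p = 0.059.
- One-sided exact: 1/32 = 0.031.
- Pratt handling of zeros, normal approximation: 0.025.
- Zeros split between signs, normal approximation: 0.54 (N = 252) to 0.57 (N = 300).

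The same five patients can therefore be significant or not according to an unstated setting.

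**B. Raw ELISA readings are tested**

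Few changes are then exactly zero, and 2/2^k does not apply. A simulation (4,000 replicates) gave every patient symmetric standard normal noise and gave k patients a rise of at least 20 noise standard deviations. Rejection rates at |z| > 1.96 were:

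| k | N = 252 | N = 300 |
|---|---|---|
| 0 | 5.1% | 4.4% |
| 5 | 7.9% | 6.9% |
| 20 | 57.1% | 49.6% |

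A hand check explains the low power at k = 5. The five largest ranks among 300 sum to 300+299+298+297+296 = 1,490. Making all five positive, instead of half on average, moves the statistic by 1,490/2 = 745. Its null standard deviation is √(300×301×601/24) = 1,504, so the shift is 745/1,504 = 0.50 standard deviations. However large the rises, rank weighting caps their effect.

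**C. The incidence summary**

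Clopper-Pearson 95% limits, with every planned patient in the denominator:
- 5/252 = 2.0% (0.6% to 4.6%)
- 5/300 = 1.7% (0.5% to 3.8%)
- 0/300 = 0%, upper limit 1 − 0.025^(1/300) = 1.2%

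This summary keeps unchanged patients in the denominator and is informative even with no events. In that case, under A, the signed-rank test has nothing to test.

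**The case against.** A reader might infer that the trial could hide antibody formation behind a non-significant p-value, or that its immunogenicity conclusion rests on this test. The documents do not support that. The same paragraph of the SAP plans listings and tables of immunogenicity data, so every positive patient would be visible. No threshold, success criterion or stopping rule refers to the laboratory p-values.

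A reader might also infer that no HACA rate will be reported at all. That goes too far. The assay gives a qualitative result, and SAP 10.1 plans counts and percentages for categorical data with a stated denominator. Percentages positive by visit can reasonably be expected. What those general rules do not supply is a definition of treatment-emergent HACA or an interval.

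A third tempting reading is that five or fewer seroconversions can never reach significance. That holds only for the exact, two-sided 5%, zeros-dropped test. An uncorrected normal approximation gives 0.043 at five.

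It can also be said that the test sentence was meant for numeric laboratory values only, because a positive/negative result has no natural numerical change. That is possible. But HACA is also measured quantitatively, and the list carries no exemption, so the text at least needs clarifying.

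Finally, no screening positivity rate is given, and exposure to murine or chimeric antibodies in the preceding 5 years is an exclusion. Offsetting falls in titre may therefore be rare.

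**Conclusion.** The point stands as a minor one. As written, SAP 10.4.2 brings HACA under a test of central shift that does not estimate the share of patients who form antibodies, and that test is the only inference named for HACA. In the exact, two-sided 5%, zeros-dropped form it ignores patients who stay negative and needs at least six seroconversions to be able to reach significance. On raw readings with symmetric noise it rejects about 7% to 8% of the time with five clear seroconverters, against about 5% with none. Either way, a non-significant result says little about immunogenicity.

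The assumptions are a 5% two-sided level for laboratory tests, application of the test sentence to every data type listed, and the noise model used for raw readings. The efficacy endpoints are unaffected. The gap is the lack of a defined treatment-emergent incidence with a confidence interval.

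**What to change.** In SAP 10.4.2, exempt immunogenicity from the signed-rank test and add a short paragraph that specifies:
- **Event:** treatment-emergent HACA, meaning negative at screening and positive at any post-dose sample, or, if positive at screening, a titre rise above a factor prespecified from the assay validation. The documents do not give that factor; it has to be taken from the validation before analysis.
- **Denominator:** patients with a screening sample and at least one post-dose sample. State how many dosed patients this leaves out, since the protocol asks for the Day 42 visit and the repeat test at the final visit only where feasible.
- **Summary:** n/N and percentage with a Clopper-Pearson 95% CI, and a listing of titres.

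If the signed-rank test is kept for the numeric laboratory values, state its level, sidedness, p-value type and handling of zeros.

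The cost is one SAP paragraph and one table. The samples are already scheduled, and no new data, visits or efficacy analyses are involved.

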10.4.3 ECG results

ECG results data will be provided in a listing and summarized in a table by time point. Clinical significance will be presented as a flag on the ECG listings and summary table will be provided.

10.5 Analysis of Efficacy

10.5.1 Primary and Key Secondary Variables (Sensitivity and Specificity)

Within this trial, two co-primary endpoints (sensitivity and specificity) shall be analysed for each reader.

The analysis for sensitivity uses only those patients with a positive histopathological diagnosis of clear cell renal cell carcinoma. These are expected to be about 70% of the included patient population. Sensitivity of ⁸⁹Zr-TLX250 will be considered adequate if the **lower boundary of a 95% Wilson (score) confidence interval for sensitivity is higher than 0.7** for at least the same two of three independent readers.

The analysis for specificity uses only those patients with a negative histopathological diagnosis of clear cell carcinoma. These are expected to be about 30% of the included patient population. Specificity of ⁸⁹Zr-TLX250 will be considered adequate if **the lower boundary of a 95% Wilson (score) confidence interval for specificity is higher than 0.68** for at least the same two of three independent readers. Two-sided tests will be consistently used in the evaluation.

To account for multiplicity and to control Type I error under the paradigm of two co-primary endpoints sensitivity and specificity will each be estimated at the 5% significance level. For the study to be deemed successful, the lower limit of the 95% Wilson confidence interval for both sensitivity and specificity must exceed their respective pre-specified thresholds.

Assuming the null hypothesis is rejected for both co-primary endpoints, formal statistical testing will proceed to the family of Key Secondary Endpoints (i.e., sensitivity and specificity in the cT1a group). Within this family, the fixed-sequence method will first assess sensitivity, followed by specificity. Results pertaining to specificity will only be considered formal evidence if the null hypothesis pertaining to sensitivity is rejected.

10.5.2 Standard Uptake value (SUV)

Standard uptake value will be analysed as described in section 9.2.2 for each reader to determine 3 cut off values and corresponding sensitivities and specificities. SUV data will be provided in tables and listings.

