
Plan for statistical analysis
	
To take multiple testing for the two co-primary endpoints into account, testing will occur in a strictly sequential order. Firstly, the observed sensitivity will be compared against a predefined minimum expected threshold for sensitivity, using a binominal confidence interval. If the null hypothesis for sensitivity testing can be rejected, the test for specificity is performed using the same methodology, applying a predefined threshold for specificity. This strategy ensures a global level of significance of <math>p < 0.05</math>.
 
Reader variability, as the most important secondary objectives will be determined using Kappa statistics.
 
All other secondary variables will be analysed descriptively using exploratory statistics.

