3.2 Secondary Objectives

Key secondary objectives of this study will be:

1. To determine sensitivity of ⁸⁹Zr-TLX250 PET/CT imaging to detect ccRCC in the subgroup of patients with indeterminate renal masses of ≤ 4 cm in largest diameter (cT1a)
2. To determine specificity of ⁸⁹Zr-TLX250 PET/CT imaging to detect ccRCC in the subgroup of patients with indeterminate renal masses of ≤ 4 cm in largest diameter (cT1a)
3. Other Secondary objectives of this study will be: To determine positive predictive value (PPV), negative predictive value (NPV), and accuracy of ⁸⁹Zr-TLX250 PET/CT imaging to detect ccRCC in patients with indeterminate solid renal masses, and in patients with indeterminate renal masses of ≤ 4 cm (cT1a)
4. To identify a standardized uptake value (SUV) cut-off for ⁸⁹ZrTLX250, suitable to discriminate ccRCC from non-ccRCC
5. To determine inter-reader variability of diagnostic assessments of ⁸⁹Zr-TLX250 PET/CT images, when performed by multiple readers
6. To determine intra-reader variability of diagnostic assessment of ⁸⁹Zr-TLX250 PET/CT images
7. To establish safety and tolerability of ⁸⁹Zr-TLX250 in patients with indeterminate renal masses.
8. To evaluate sensitivity and specificity of ⁸⁹Zr-TLX250 PET/CT imaging to detect ccRCC in patients with IRMs ≤ 3 cm, IRMs ≤ 2 cm, and Bosniak 3 and 4 lesions.

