4.2 Secondary Endpoints

Key secondary endpoints include the determination of the study drug's potential to detect ccRCC in IRMs ≤ 4 cm in largest diameter (tumour stage cT1a), and secondary endpoints include determination of predictive values (standard uptake values (SUVs)) of PET signals in the kidney in CT1 and cT1a patients. Moreover, the reproducibility of the qualitative visual assessment of tumour targeting will be determined and safety and tolerability will be assessed.

Reading for the co-primary endpoints (sensitivity and specificity) will be conducted independently by three trained central readers, blind to history, and histology results. Inter-reader concordance will be assessed using kappa statistics. Similarly, kappa statistics will be used to assess intra-reader variability, using a subset of 10% of randomly selected cases read twice by individual readers.

⁸⁹Zr-TLX250 SUVs will be determined for each tumour lesion. Receiver operating characteristics (ROC) will be analysed to identify a SUV cut-off value most appropriate to discriminate between ccRCC or non-ccRCC as evidenced by central histology results.

⁸⁹Zr-TLX250 activity and antibody mass concentrations in tumour at the time of imaging (MBq/cm³, mg/cm³) will be determined, considering the absolute activity bound to the tumour, lesion volume as determined by CT/MRI, and the decay-corrected specific activity, using a general model of average girentuximab kinetics in tumour over time (derived from sequential ⁸⁹Zr-TLX250 biodistribution data from earlier studies).

A sub-group analysis will evaluate sensitivity and specificity of ⁸⁹Zr-TLX250 PET/CT imaging to detect ccRCC in patients with IRMs ≤ 3 cm, IRMs ≤ 2 cm, and Bosniak 3 and 4 lesions.

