5 STUDY DESIGN AND SCHEDULE OF ASSESSMENTS

5.1 Study Design

This will be a confirmatory, prospective, open-label, multi-centre phase 3 study (ZIRCON) in adult patients with pre-study imaging evidence of indeterminate renal masses (IRM) of ≤ 7 cm in largest diameter, and scheduled for partial or total nephrectomy as part of their standard of care. The study is designed to evaluate sensitivity and specificity of ⁸⁹Zr-TLX250 PET/CT imaging to non-invasively detect clear cell renal cell cancer (ccRCC).

Histological confirmation will serve as standard of truth, to assess sensitivity, specificity, positive predictive value (PPV), negative predictive value (NPV), as well as accuracy of ⁸⁹Zr-TLX250 PET/CT imaging. Consequently, this study will be conducted in patients with IRM of stage cT1, in which histological material is obtained as part of routine nephrectomy, circumventing the need for study-specific invasive procedures. Given a reported high rate of non-diagnostic kidney biopsies, patients scheduled to undergo kidney biopsy only, rather than nephrectomy are not eligible for this study.

Approximately 252 adult patients were originally planned to be recruited in 35 – 40 renal cancer care specialist centres in Europe (Belgium, France, Spain, the Netherlands), UK, Turkey, Australia, Canada and USA, who have access to state-of-the-art PET/CT imaging. The number of enrolled patients was increased to 300 by a protocol version 8 amendment 7 to ensure adequate precision in measuring both sensitivity and specificity of ⁸⁹Zr-TLX250PET/CT imaging.

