8.3 Screening Analysis Set

The Screening Analysis Set (for CONSORT-style accounting of subject disposition) will consist of all patients assigned a Patient Number.

All primary and secondary efficacy analyses will be carried out using the FAS.

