9.2.2 Standardised Uptake Value (SUV)

⁸⁹Zr-TLX250 SUVs will be determined for each tumour lesion. Receiver operating characteristics (ROC) will be analysed, to identify a SUV cut-off value, most appropriate to discriminate between ccRCC or non-ccRCC as evidenced by central histology results.

$$\text{SUV} = C_{\text{image}} / (\text{injected dose} / \text{body weight})$$

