10.5.3 Predictive values and accuracy

Secondary efficacy will be analysed using positive predictive values, negative predictive values and accuracy for each of the three readers. Computation of the values is shown in the section 9.2.1

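### SAP 10.5.2 states no optimism correction for sensitivity and specificity at its ROC-derived SUV cut-offs, so on the natural reading they are apparent values (minor)

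*SAP*

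**What the plan says.** Objective 4 in SAP 3.2 is "To identify a standardized uptake value (SUV) cut-off" that separates ccRCC from non-ccRCC; Protocol 2.2 has the same objective. SAP 9.2.2 and Protocol 9.1.2.2 give the method: ROC analysis "to identify a SUV cut-off value, most appropriate to discriminate between ccRCC or non-ccRCC as evidenced by central histology results". What makes a cut-off most appropriate is not defined.

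SAP 10.5.2 refers back to SAP 9.2.2 and applies it "for each reader to determine 3 cut off values and corresponding sensitivities and specificities". On the data used, SAP 8.3 states: "All primary and secondary efficacy analyses will be carried out using the FAS". Neither document mentions a split sample, cross-validation, bootstrap or external data set for the SUV cut-off.

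On status, the synopsis of the protocol (plan for statistical analysis), having singled out reader variability, says: "All other secondary variables will be analysed descriptively using exploratory statistics". Protocol 8.2.2.1 bases the positive or negative PET call on visual reading alone.

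**The concern.** A cut-off chosen because it performs best in a sample will, on average, look better in that sample than in new patients. If sensitivity and specificity are read off the same ROC curve that supplied the cut-off, they carry this optimism, and an ordinary confidence interval around them does not reflect it. Specificity suffers more because fewer patients are non-ccRCC.

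What is at stake is later reliance on the SUV cut-off. An objective to find a suitable threshold is of use only if its stated accuracy carries over to patients outside the trial.

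The size of the optimism depends on the selection criterion, and the SAP names none.

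**Working it through.** The plan gives no AUC, SUV distribution or expected SUV accuracy, so there is no figure of its own to reproduce. The check asks how large the optimism would be.

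**Inputs from the documents.** SAP 7 assumes 70% cT1a and 30% cT1b, with non-ccRCC rates of 34% and 17%. The non-ccRCC share is 0.7 × 0.34 + 0.3 × 0.17 = 0.289. SAP 7 gives 252 patients; SAP 5.1 says "The number of enrolled patients was increased to 300 by a protocol version 8 amendment 7".
- 252 × 0.289 = 72.8, so 73 non-ccRCC and 179 ccRCC.
- 300 × 0.289 = 86.7, so 87 non-ccRCC and 213 ccRCC.

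**Assumptions not in the documents.** SUV (on some scale) is N(0, 1) in non-ccRCC and N(d, s²) in ccRCC, with s = 1.0 or 1.5 and d set so that AUC = Φ(d / √(1 + s²)) runs from 0.80 to 0.95. There were 4000 simulated trials per setting.

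**Calculation.** In each trial a cut-off c is chosen by one of three rules:
- Youden: maximise Se + Sp.
- Closest-to-corner: minimise (1 − Se)² + (1 − Sp)².
- Fixed sensitivity: hold the sample sensitivity at 90%.

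True values at the chosen c are Se = 1 − Φ((c − d)/s) and Sp = Φ(c). Optimism is the mean of apparent minus true.

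Optimism in points (sensitivity / specificity), 87 non-ccRCC and 213 ccRCC, s = 1.0:

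| Rule | AUC 0.80 | AUC 0.85 | AUC 0.90 | AUC 0.95 |
|---|---|---|---|---|
| Youden | 1.39 / 3.38 | 1.23 / 3.02 | 1.14 / 2.84 | 0.94 / 2.40 |
| Closest-to-corner | 0.99 / 2.40 | 0.97 / 2.36 | 0.90 / 2.10 | 0.79 / 1.78 |
| Fixed 90% sensitivity | 0.31 / 0.14 | 0.28 / 0.28 | 0.36 / 0.21 | 0.28 / 0.28 |

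Range over both sample sizes and both values of s:
- Youden: sensitivity 0.9 to 1.5, specificity 2.3 to 3.7.
- Closest-to-corner: 0.7 to 1.2 and 1.8 to 2.9.
- Fixed 90% sensitivity: 0.3 to 0.4 and 0.1 to 0.4.

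The convention for placing candidate cut-offs moves these by a few tenths of a point. A separate Youden run at AUC 0.91, where the best cut-off has 83% for both measures, gave apparent 84.1 / 84.8 against true 83.0 / 82.0 at 300 patients.

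**Scale.** The Wilson 95% half-width is z√(p(1 − p)/n + z²/4n²) / (1 + z²/n). With p = 0.83 it is 5.0 points at n = 213 and 7.8 at n = 87.

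**Does a correction work?** For each resample (drawn within histology group), re-select the cut-off and take its accuracy in the resample minus its accuracy in the original sample. Average this over resamples and subtract it from the apparent value. Results with 400 trials × 300 resamples (Se / Sp, %):

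| Setting | Apparent | Corrected | True | Left over |
|---|---|---|---|---|
| 87/213, AUC 0.80, Youden | 73.8 / 74.9 | 72.8 / 72.5 | 72.4 / 71.3 | 0.4 / 1.2 |
| 87/213, AUC 0.80, corner | 73.9 / 74.0 | 73.1 / 72.2 | 73.0 / 71.4 | 0.1 / 0.8 |
| 87/213, AUC 0.90, Youden | 82.9 / 83.9 | 82.1 / 81.9 | 81.7 / 80.9 | 0.4 / 1.0 |
| 87/213, AUC 0.90, corner | 83.1 / 82.9 | 82.5 / 81.4 | 82.3 / 80.8 | 0.2 / 0.6 |
| 73/179, AUC 0.90, Youden | 82.8 / 84.2 | 81.9 / 82.0 | 81.5 / 80.8 | 0.4 / 1.2 |
| 87/213, AUC 0.90, fixed 90% Se | 90.1 / 70.0 | 89.8 / 69.8 | 90.0 / 69.8 | −0.2 / 0.0 |

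For the optimising rules most of the optimism goes. In the first row, for example, specificity optimism falls from 74.9 − 71.3 = 3.6 to 1.2. Under fixed sensitivity there is nothing useful to correct.

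**The case against.** The strongest reply is that objective 4 is to identify a cut-off, not to validate one. The analysis is descriptive, with no alpha, threshold or success rule attached, and the SAP does not claim that the SUV accuracies hold in new patients. The optimism is smaller than the sampling error. The correction also buys little in total error: under Youden at 87/213 and AUC 0.90, root-mean-square error around true accuracy fell only from 2.8 to 2.6 points for sensitivity and from 4.7 to 4.2 for specificity. This stands as a limit on severity, and it supports making the bootstrap conditional on an optimising criterion. It does not remove the point: descriptive status excuses the lack of alpha control, but it does not make an apparent accuracy an unbiased one, and the error runs in one direction.

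Three stronger readings are tempting, and the documents do not support them.
- **That the trial's main result is inflated.** PET status is visual, so no SUV cut-off enters the co-primary or key secondary endpoints.
- **That the SAP calls for nine cut-offs and contradicts its objective.** The phrase can be read as three per reader, but SAP 10.5.2 cites SAP 9.2.2, which speaks of one cut-off, and there are three readers. One per reader is the natural reading. By-reader reporting is also the trial's consistent design: SAP 10.5.3 likewise gives predictive values and "accuracy for each of the three readers". What remains open is how three reader-specific values answer an objective framed around one.
- **That the SAP prescribes uncorrected same-sample evaluation.** It does not say so; this is an inference from silence, though no passage points to another method.

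**Conclusion.** The concern holds as a minor point. With one analysis set and no correction stated, sensitivity and specificity at the SUV cut-offs are most naturally read as apparent values. Whether that matters in practice turns on the unnamed criterion: a modest overstatement, mainly of specificity, under an optimising rule, and practically none under fixed sensitivity.

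These sizes rest on assumed binormal SUVs, the stated AUC range, and the SAP's planning rates for case mix. SAP 4.2 also refers to "determination of predictive values (standard uptake values (SUVs)) of PET signals in the kidney in CT1 and cT1a patients". If that means the cut-off is derived in cT1a alone (252 × 0.7 × 0.34 = 60 non-ccRCC and 116 ccRCC, or 71 and 139 at 300), Youden optimism would be 1.2 to 2.2 points for sensitivity and 2.4 to 4.1 for specificity. The sentence is too loosely worded to rely on for this.

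**What to change.** In SAP 10.5.2, keep the by-reader analysis and add: if the cut-off is chosen by an optimising criterion, sensitivity and specificity at the cut-off will be reported for each reader after a bootstrap optimism correction in which the cut-off is re-selected in every resample, and uncorrected values will be labelled apparent. Under a fixed-sensitivity rule the label is enough.

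As wording only:
- Confirm that the three cut-offs are one per reader.
- Name the ROC criterion, which is the sponsor's choice, before the SUV data are analysed.
- Say which value answers objective 4.

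A bootstrap confidence interval for the cut-off is optional.

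The cost is a few SAP lines and a standard bootstrap per reader, with no new data. The reported SUV accuracy becomes slightly less favourable. The correction is incomplete: in the check above, specificity stayed about 0.6 to 1.2 points optimistic under the optimising rules.
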